## **Literature review**

Social anxiety is the third most common mental health issue after depression and alcohol abuse (Aune et al., 2022), particularly for youth aged from 15 to 24 (Tang et al., 2022). From the perspective of the information processing, cognitive bias is the main cause of the occurrence and maintenance of social anxiety symptoms in youth, encompassing three aspects: attention bias, interpretation bias, and memory bias (Amir & Bomyea, 2010; Kuckertz & Amir, 2014). Specifically, youth with attention bias tend to focus on the threat-related cues in the social environment (attentional vigilance), and then quickly shift their attention away (attentional avoidance). Building on attention bias, interpretation bias may lead socially anxious youth to interpret ambiguous social information negatively and attributions negative events to internal causes (Amir & Bomyea, 2010; Haller et al., 2016; Martinelli et al., 2022). In addition, memory bias refers to the tendency to recall or recognize negative stimuli, especially self-related negative information (Kuckertz & Amir, 2014; Morgan, 2010). These three cognitive biases form a self-reinforcing circle, perpetuating and exacerbating social anxiety symptoms (Nikolić, 2020).

Current treatments for cognitive bias, such as cognitive bias modification, can only yield a significant but small and unstable effect. (Enock et al., 2014; Heeren et al., 2015; Liu et al., 2017). As a result, recent research has shifted toward targeting the underlying mechanisms to achieve more robust reductions in cognitive bias, particularly at the neural circuit level (Heeren et al., 2016). High-definition transcranial direct current stimulation (HD-tDCS) is a non-invasive brain stimulation technique that delivers direct current through electrodes placed on the scalp. This current induces polarization of neuron cell membranes, thereby enhancing or inhibiting cortical activity (Kuo et al., 2013; Stein et al., 2020). For individuals with social anxiety, they often exhibit reduced regulatory control of prefrontal cortex (PFC) over the limbic system, particularly in the left dorsolateral prefrontal cortex (DLPFC) (Cremers & Roelofs, 2016). Therefore, previous tDCS studies adopted anodal tDCS to the left DLPFC and demonstrated that both attention, interpretation and memory bias in clinical populations can be significantly improved (Heeren et al., 2016; Nejati et al., 2022; Nejati et al.,

2021).

However, most intervention studies just applied online tDCS stimulation to modify cognitive bias while overlooking its offline effects. Compared to short-term online effects, long-term offline effects are crucial for reducing intervention dependence and restoring normal social functioning. Moreover, previous studies have lacked direct tDCS interventions targeting socially anxious youth, resulting in insufficient consideration of the core characteristics and specific cognitive processing patterns associated with social anxiety. Specifically, regarding attention bias, prior studies have primarily focused on attentional vigilance while neglecting attentional avoidance (Jafari et al., 2021; Nejati & Estaji, 2024), a key characteristic of youth with social anxiety (Morales et al., 2015). In terms of interpretation bias, previous studies have failed to incorporate social contexts that may trigger negative evaluations into their measurement paradigms (Nejati et al., 2021), making it difficult to generalize findings from other clinical populations to socially anxious youth. Regarding memory bias, individuals with social anxiety tend to focus on their own performance in social situations, making them more likely to encode and retrieve self-referential negative memories. Thus, it is essential to examine tDCS effects on negative memory bias within a self-referential encoding framework. To address these gaps, the present study implemented offline tDCS stimulation and adjusted the stimulation protocol to enhance sustained intervention effects, and adopted a group-specific assessment paradigm to improve the precision of cognitive bias evaluation in socially anxious youth. In addition, while many studies have examined the effects of tDCS on attention, interpretation or memory bias individually (Jafari et al., 2021; Nejati & Estaji, 2024; Sanchez-Lopez et al., 2018; Winker et al., 2019), its influence on psychopathology symptoms remains underexplored. Given this, the current study utilized HD-tDCS as an intervention to explore changes in social anxiety symptoms.

In current study, we adopted a comparative intervention study with randomized controlled in which we delivered multiple courses of offline anodal HD-tDCS over the left DLPFC. The aim of this study was to explore the offline impact of HD-tDCS on cognitive bias (including attention, interpretation and memory bias) among youth with

social anxiety symptoms. In addition, the researchers sought to further investigate the impact of tDCS stimulation on social anxiety. We hypothesized that anodal tDCS would activate the left DLPFC to facilitate cognitive control of threat-related information among youth with social anxiety, thereby reducing threat attention, interpretation and memory bias, and even improving social anxiety symptoms.

## **Method**

### **Participants**

This study recruited youth with social anxiety symptoms from the South China Normal University in Guangdong Province, China. Participants who were: 1) aged 15 to 24 years; 2) scored above 55 and below 95 on the Liebowitz Social Anxiety Scale (the cut-off score for social anxiety in the Chinese version (Liebowitz, 1987); 3) scored below 5 on the Patient Health Questionnaire (Kroenke et al., 2001) were eligible. Those with 1) any psychiatric disorders; 2) current or past diseases or injuries related to the brain; 3) medical pumps, pacemakers and cochlear implants in the body; 4) current pharmacological or mental treatments; 5) tDCS or TMS experiences over past year were also excluded.

### **Randomized and blinding**

Participants were randomly assigned to either tDCS or sham groups using a computer-generated randomization table, with a 1:1 allocation ratio. Participants remained blinded to treatment conditions throughout the intervention period. Researchers only received allocation information immediately prior to procedure implementation.

### **Interventions and study procedures**

The whole HD-tDCS intervention process was 10 sessions for 5 consecutive days (20 minutes each session and 2 sessions a day). All participants received active or sham HD-tDCS stimulation via a device from Soterix Medical, Inc (Woodbridge, NJ, USA). According to the 10/20 International EEG System, a “4 x 1 ring set-up” was placed in F3, FP1, FT7, C3 and FZ. F3 is the central anode electrode, which refers to the left

DLPFC, surrounded by the other 4 return cathode electrodes (Heeren et al., 2016; Jafari et al., 2021; Liu et al., 2023; Müller et al., 2022; Nejati et al., 2021; Parlikar et al., 2021). Both the tDCS group and the sham group were given electric current at the same electrode position. Normally, the current gradually rose to 2mA for the first 30 seconds, then continued for 20 minutes and then dropping to 0mA at the end of the stimulation. In the sham group, the current ramped up to 2mA for 30 seconds at the start and end of the stimulus and then ramped down without the participants' being aware of it, generating the same sensation as the active condition. During the intervention, participants were asked to maintain a relaxed and immobile posture.

Prior to the study, participants completed an enrollment screening questionnaire to determine their suitability for tDCS intervention. Participants who met the inclusion criteria were randomly divided into the tDCS and the sham group. Both two groups received 10 sessions of stimulation with 3 hours intervals between daily sessions (2 sessions daily, 5 days in total). Psychological symptoms (including social anxiety symptoms, cognitive bias and trait anxiety) and cognitive bias task performance (including dot probe task, word-sentence association paradigm, free recall and recognition task) were assessed before the first tDCS stimulation (pre-test) and after the last tDCS stimulation (post-test). According to the Latin square, the order of the three cognitive bias tasks was randomly counterbalanced among the participants. Finally, in order to ensure the safety of the tDCS stimulation and to compare the perception of this stimulation between different groups, a side-effect checklist was filled out by the participants after each session of stimulation. In addition, psychological symptoms were assessed again at 4 weeks follow-up. Participants in the entire experiment were rewarded with 280 RMB.

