### **Sample Size Calculation**

The required sample size was calculated using G\*Power software. Based on repeated measures analysis of variance, the sample size for each group was at least 27 (effect size = 0.25,  $\alpha$  = 0.05, power = 0.95). To avoid the impact caused by loss, an additional 10 people were included in each group, that is, 37 people. A total of 74 people

were recruited in two groups.

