### **Data preparation and statistical analysis**

Before formal analysis, this study addressed errors and outliers in the three tasks, respectively. Trials with incorrect reactions and with RTs greater than 3000ms, lower than 200ms, or greater than  $\pm 3$  standard deviation were excluded when calculating each participants' task performances. We also treated attention, interpretation and memory bias index of  $\pm 3$  standard deviation as extreme values.

Firstly, group differences across these two groups were measured using t-tests for scale and behavioral variables, and Chi-square tests for sociodemographic variables. To explore the intervention effect of tDCS on task performance, repeated-measures ANOVA were conducted with "group" (tDCS vs. sham group) as the between-subject and "time" (pre-test vs. post-test) as the within-subject factors. The outcomes of dot probe task, word sentence association paradigm and free recall and recognition task served as dependent variables. Before the ANOVA analysis, we used the Levene test to evaluate the homogeneity of variance of the data and the results showed that the data basically satisfied the homogeneity of variance hypothesis. The Bartlett and Mauchly's test were also performed to assess the sphericity of the data, and the degrees of freedom were modified by the Greenhouse-Geisser approach if needed. For subjective scale data, we employed 2-level linear mixed-effects regression, which included three fixed effects (group, time and the interaction between group and time) and one random effect (participants). All of these analyses were conducted using SPSS 25.0 and R software. The significance level was set at  $p < 0.05$ , and the marginal significance level was set at  $p < 0.1$ . Effect sizes were reported by the partial eta-squared ( $\eta^2$ ) for ANOVA, and the Cohen's d for pairwise comparisons.

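### Task order is varied by Latin square but left out of the task ANOVAs, and the plan does not say whether order was balanced within arm or kept at post-test: a minor loss of precision, not a bias

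*Combined protocol and SAP*

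**What the plan says.** Under Interventions and study procedures, task order is a factor that the design itself imposes: "According to the Latin square, the order of the three cognitive bias tasks was randomly counterbalanced among the participants". The same section places the tasks before the first and after the last stimulation. It does not give the number of orders, the level at which they were balanced (overall or within arm), whether a participant had the same order at both visits, or the interval between the last stimulation and the post-test tasks.

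Under Randomized and blinding, arms were assigned "using a computer-generated randomization table, with a 1:1 allocation ratio", with no mention of task order.

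Under Data preparation and statistical analysis, "repeated-measures ANOVA were conducted with 'group' (tDCS vs. sham group) as the between-subject and 'time' (pre-test vs. post-test) as the within-subject factors". The dependent variables are the outcomes of the three tasks. Order is not a factor, a covariate or a sensitivity analysis.

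**The concern.** Counterbalancing spreads order effects over participants, but their variance leaves the error term only if order is in the model. With two visits, the group x time test is a two-sample test on the post-minus-pre change, so what matters is any effect of order on change.

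Such an effect can arise in two ways. The effect of position may differ between visits: post-test comes after stimulation and pre-test before any, so time since stimulation could depend on position at post-test only. Or the order may have been redrawn at post-test, in which case position effects from both visits enter the change. The plan rules out neither. At stake is precision on the cognitive outcomes, which could be recovered almost free if each participant's order was recorded.

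**Working it through.** **1. The plan's own figure.** Sample Size Calculation gives an effect size of 0.25, alpha 0.05, power 0.95 and at least 27 per group, raised to 37 per group (74 in total) for loss. For the group x time interaction, with two groups and m = 2 visits, power comes from a noncentral F on 1 and N − 2 degrees of freedom with λ = f² × N × m / (1 − ρ). The plan does not state the pre-post correlation ρ; I assume 0.5. At N = 54, λ = 0.0625 × 54 × 2 / 0.5 = 13.5 and power is 0.950; N = 52 gives 0.942. So 27 per group reproduces. In change-score terms λ = (N/4) × (Δ/SD of change)², so 13.5 corresponds to Δ = 1.0 SD of change. At N = 74 power is 0.989.

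**2. Is a position-dependent difference plausible?** The stated timings give:
- dot probe: 120 × (0.5 + 0.5 + RT + 1.5) s, or 5.6 to 6.2 min for an assumed RT of 0.3 to 0.6 s;
- word sentence association: 60 × 3.0 s = 3.0 min or more;
- memory task: 75 + 180 + 120 + 240 s = 10.25 min or more.

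A task done third therefore starts about 9 min (memory) to 16 min (word sentence association) later than if done first. That makes a position effect possible; it does not show one.

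**3. Variance added to the change.** Assume three equally frequent positions, a first-to-third difference of d outcome SDs coded −d/2, 0, +d/2, and equal SDs. With ρ = 0.5 the variance of change is 2(1 − 0.5) = 1. The coded effect has variance (d²/4 + 0 + d²/4)/3 = d²/6.
- Order kept, effect the same at both visits: it cancels and adds 0.
- Order kept, the whole of d being an order-by-time effect: adds d²/6.
- Order redrawn independently at post-test, effect d at each visit: adds 2d²/6.

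**4. Power for 1.0 SD of change**, with λ divided by (1 + added variance):

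| d | Added variance, kept / redrawn | 27 per arm, kept / redrawn | 37 per arm, kept / redrawn |
|---|---|---|---|
| No effect on change | 0 | 95.0% | 98.9% |
| 0.3 | 1.5% / 3% | 94.7% / 94.4% | 98.8% / 98.7% |
| 0.5 | 4% / 8% | 94.2% / 93.4% | 98.6% / 98.3% |
| 0.8 | 11% / 21% | 92.9% / 90.5% | 98.1% / 97.1% |

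The 'kept' entries apply only if all of d is an order-by-time effect. For a smaller treatment effect, 0.5 SD of change at 37 per arm, power is 56.4%; at d = 0.8 it becomes 52.3% (kept) or 48.7% (redrawn).

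**5. Chance imbalance.** If three orders were balanced only overall (25/25/24) and arms of 37 were drawn independently, the largest between-arm difference in any one order has median 5 and 95th percentile 9 participants. It is 5 or more with probability 54%, and 7 or more with probability 27%. At d = 0.5 on change, the resulting shift in the group difference has SD of about 0.05, against a standard error of √(2/37) = 0.23.

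**6. Bias and type I error.** I simulated 37 per arm, 10,000 runs per setting, with a larger order effect of −0.5/0/+0.5 SD (first-to-third 1.0 SD) balanced overall. Mean bias was about 0 throughout. Type I error was 0.052 (stable effect, order kept), 0.052 (order-by-time effect added) and 0.049 (redrawn). For a true effect of 0.75 SD, power was 0.888 with no order effect, and 0.887, 0.836 and 0.795 in those three settings. The stable, kept case loses nothing beyond simulation noise.

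**7. Cost of adjusting when order has no effect.** At 27 per arm, error degrees of freedom fall from 52 to 50 and power from 0.9501 to 0.9498.

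**The case against.** The strongest case on the other side is that this is largely a matter of preference. Counterbalancing followed by an unadjusted analysis is valid, a stable order effect cancels in the contrast of interest, and at the 74 recruited the worst case examined costs under 2 points of power. The order-effect sizes have no source in the documents. All of that stands, and it is why the point is minor.

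Several stronger readings are tempting and should be resisted:
- **That order was not balanced within arm.** The text says only that it was balanced among participants, which does not exclude balancing within arm. The 54% and 27% figures depend on that inference.
- **That there were exactly three orders.** A Latin square is named, but no number of orders is given.
- **That chance imbalance biases the comparison.** Under randomisation it is ordinary random error, already reflected in the standard error.
- **That the post-test tasks directly follow a 20-minute session.** No interval is stated, so an order-by-time effect is possible but not documented.

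It is also fair to object that the plan is written in the past tense, with recruitment described as done, so orders may no longer be reassignable. And a single between-subject order factor would not remove position effects if order was redrawn. Both objections are right and shape the fix.

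They do not remove the point. The plan is silent on whether order was kept, so cancellation cannot be assumed, and the adjustment costs almost nothing.

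**Conclusion.** The point holds as a minor, nearly free gain in precision and a gap in reporting. The task ANOVAs omit a factor that the design imposes, and the plan does not give the information needed to tell whether the omission matters.

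The loss is zero if the order effect is stable and the order kept. Otherwise, at the plan's own effect size, it is about 0.3 to 4.5 points of power at 27 per arm and at most about 2 points at 37 per arm. These figures rest on assumed order effects of 0.3 to 0.8 SD, ρ = 0.5, equal SDs and three equally frequent positions; none of these is given in the documents. A reader might infer that the tDCS-sham comparison is biased or its p-values invalid. Neither the documents nor the calculations support that.

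**What to change.** In Data preparation and statistical analysis, add task order, with as many levels as the Latin square used, and order x time to each task ANOVA. Leave out a group x order term and keep group x time as the test of effect. If order was redrawn at post-test, adjust instead for the task's position at each visit, for example in a mixed model with position as a visit-level covariate. If the outcome data have already been analysed, label the adjusted model as a sensitivity analysis beside the stated one, so that it does not become a choice between results.

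In Interventions and study procedures, state the number of orders, balance them within arm and keep each participant's order at both visits. If assignment is finished, report instead the number of participants per order in each arm and whether order was kept.

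The cost is a sentence or two in each section and, with three orders, 2 error degrees of freedom: under 0.1 point of power if order has no effect. More orders would use more degrees of freedom. No new participants or assessments are needed, but each participant's order must have been recorded, which the plan does not confirm.

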### **Sample Size Calculation**

The required sample size was calculated using G\*Power software. Based on repeated measures analysis of variance, the sample size for each group was at least 27 (effect size = 0.25,  $\alpha$  = 0.05, power = 0.95). To avoid the impact caused by loss, an additional 10 people were included in each group, that is, 37 people. A total of 74 people

were recruited in two groups.

## Assessments and outcomes

### *Questionnaires*

The Liebowitz Social Anxiety Scale (LSAS) was used to distinguish participants with social anxiety (defined as an LSAS score  $\geq 55$ ) and assess the changes of anxiety symptoms between pre- and post-tDCS intervention. This scale involves 24 Likert-items with higher score indicating severe social anxiety (Gong et al., 2023; Liebowitz, 1987). The Patient Health Questionnaire (PHQ-9) was only used to screen those without depression. The total score of the nine items was calculated, ranging from 0 to 27, with a cut-off score of 5 (Kroenke et al., 2001; Wang et al., 2014). In addition, participants also completed the Negative cognitive processing bias questionnaire (NCPBQ) and the Spielberger Trait Anxiety Inventory - Trait (STAI-T). The NCPBQ consists of 17 items divided into three subscales with three lie detection items: a 5-item attention bias, a 5-item interpretation bias and a 4-item memory bias. It was measured using a 5-point Likert scale from 1 (“disagree completely”) to 5 (“agree completely”). A higher score represented a higher level of cognitive bias (Miao et al., 2022; Zhang, 2015). The STAI-T is an inventory concerning and evaluating trait anxiety. There are 20 items with 4-point Likert style from 1 (“not at all”) to 4 (“very much”) (Spielberger et al., 1971). All of these questionnaires in this study have high reliability (Cronbach’s alpha  $> 0.80$ ).

Some sociodemographic information was also collected, with sex, ethnicity, residence and only-child status as binary variables, and socio-economic level, relationship with parents and family harmony as continuous variables.

### *Dot probe task*

Dot probe task is a common experimental paradigm for measuring attention bias (MacLeod et al., 1986). After appearance of a fixed cross in the center of the computer screen, a pair of faces appear side by side. Then, a probe appears on the location previously occupied by one of the two faces. Participants were asked to response the location of the probe as quickly as possible and press the appropriate keys to answer. If the probe was presented at a location that matched the attention, participants would

response more quickly than the mismatched location. In current study, the experimental task included 40 facial stimuli (20 male and 20 female), forming 30 face pairs (20 neutral-angry and 10 neutral-neutral combinations). Based on valence scores from preliminary testing, angry faces were categorized as either high-intensity and low-intensity. All these faces were selected from the Chinese facial affective picture system (Gong et al., 2011). The number of trials for each type of stimuli location (left or right) and probe location (left or right) were equal. And a total of 120 trials were delivered in one block (120 trials = 30 face-pairs \* 2 face locations \* 2 probe locations). The fixed cross appeared for 500ms and then a pair of facial stimuli (neutral-angry or neutral-neutral) appeared for 500ms. The probe (“\*”) then appeared and remained until a response (“F” for left and “J” for right) was made. The inter-trial interval was 1500ms.

This study used the trail-level bias score (TL-BS) as a measure of the main outcomes of this task (Zvielli et al., 2015). TL-BS is an indicator of reaction time (RT), calculated by subtracting contiguous pairs of congruent trials (probe and emotional face appeared on the same location of the screen) from incongruent trials (probe and emotional face appeared on the opposite location of the screen). Positive scores represent a tendency to be alert and attentive to emotional faces, while negative scores represent avoidance of these stimuli. A score close to zero indicated a balance of attention to emotional and neutral faces. Specifically, there are 4 TL-BS parameters: (1) Mean TL-BSpositive indicates the average value of TL-BSs > 0ms; (2) Mean TL-BSnegative indicates the average value of TL-BSs < 0ms; (3) Peak TL-BSpositive indicates the maximum TL-BS value; (4) Peak TL-BSnegative indicates the minimum TL-BS value.

